## 6.0 Statistical Considerations and Analysis

### Primary Endpoint

The goal of this study is to determine if 3D image guided treatment planning allows for improved tumor coverage while respecting normal tissue constraints as compared to standard 2D treatment planning. To address this, the D90 (or the dose to 90% of the HR-CTV volume) and maximally irradiated 2 cc of the bladder (D2 cc bladder) and rectum (D2 cc rectum) will be compared (these parameters have been reported in the past to correlate with toxicity).

To better understand the dose distribution the other parameters listed in Table 2 will also be documented and compared for each of the three plans described above.

### Sample Size

Preliminary data were collected on 4 patients who received MRI with the brachytherapy applicator in place. After the patient was treated a GEC-ESTRO MRI based manually optimized plan was created and compared to the 2D plan. Data for HR-CTV D90 and maximally irradiated 2 cc of bladder and rectum were collected. The paired differences in the 3 parameters of interest were:

- HR-CTV D90 - mean difference of 459.91 cGy with a standard deviation of 303.69 cGy. The mean HR-CTV 90 for the standard film method was 1368.73 cGy.
- D2 cc bladder – mean difference of 407.11 cGy with a standard deviation of 250.81 cGy. The mean D2 cc bladder for the standard film method was 1474.44 cGy.
- D2 cc rectum – mean difference of 159.83 cGy with a standard deviation of 194.44 cGy. The mean D2 cc rectum for the standard film method was 962.50 cGy.

We would like to demonstrate an improvement (i.e., increase) in HR-CTV D90 of at least 20% (i.e., at least 273.75 cGy) with MRI based planning over standard 2D planning. With a sample size of 30 patients we will have 96% power with a 2-sided significance level of 0.0056 to detect an improvement of at least 20% in the HR-CTV D90 with the MRI guided procedure using a t-test.

With a sample size of 30 patients we will have 90% power to detect an increase in D2 cc bladder of 0.80 standard deviations, or 200 cGy (i.e., 14.4%) with a 2-sided significance level of 0.0056 using a t-test.

With a sample size of 30 patients we will have 90% power to detect an increase in D2 cc rectum of 0.80 standard deviations, or 155 cGy (i.e., 16.1%) with a 2-sided significance level of 0.0056 using a t-test.

We use the Bonferroni correction to the significance level since we are testing 3 methods  $\times$  3 dosimetry parameters = 9 hypotheses (e.g.,  $0.05/9 = 0.0056$ ). These sample size calculations were performed using nQuery Advisor ® 7.0 (Copyright ©

1995-2007, Statistical Solutions, Saugus, MA).

We anticipate that 25% of patients will not be evaluable due to inability to accommodate an MRI compatible applicator. In addition, we anticipate that 30% of patients will receive tandem and cylinders or non-adaptive tandem and ovoids. The applicator type used significantly alters the dose distribution which is expected to impact the relative dosimetric benefit of MRI. As a result, the primary analysis will be limited to patients with the adaptive, shielded ovoid, which is the most commonly used applicator in non-protocol patients. We would therefore like to accrue a total of 57 patients in order to achieve our goal of 30 evaluable patients treated with the adaptive tandem and ovoid system.

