### Contouring and Treatment Planning

As is standard, our dosimetrists will develop a 2D plan according to the loadings recommended by the physician based on the physical examination, initial diagnostic imaging ,and orthogonal films. As is routine the treating physician will then evaluate the 2D plan looking at doses to specific points (rectal and bladder) delineated on the 2D imaging and make adjustments as they see fit. Following acquisition of both MRI and CT and finalizing of the 2D treatment plan, images will be reviewed by the treating physician before treatment to rule out any possible rare major deviations in applicator placement such as uterine perforation. The 3D imaging will also be used to inform the physician prescribing the dose of the location and size of any residual disease and

location of critical organs such that they may make subtle adjustments to the 2D treatment plan. Based on this a new plan, 2D plan informed by 3D imaging, will be created, and the patient will be treated with this plan.

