#### Dosimetric Treatment Planning Study

The first plan will be a CT based plan and will be optimized to improve the HR-CTV D90 (dose received by 90% of the target volume) to as close to 85 Gy as possible without exceeding the known tolerance dose to rectum and bladder (D2cc of rectum  $\leq$  70 Gy and D2cc of bladder  $\leq$  90 Gy). The second plan will be optimized the same as the first but with the HR-CTV, rectum, and bladder delineated on MRI instead of CT.

Table 1

Plan	Description
1) 2D Plan	This will be based on the standard loadings recommended by the physician after performing physical exam at time of implant and review of orthogonal films delineating applicator placement. The initial diagnostic imaging will be reviewed and help to inform this plan and adjustments will be made based on point doses.
2) 2D Plan informed by 3D images at time	This will be based on the standard loadings

of implant.	recommended by the physician after performing physical exam at time of implant and review of orthogonal films delineating applicator placement. The initial diagnostic imaging as well as the MRI and CT scan at the time of implant will be reviewed and help to inform this plan. The patient will be treated with this plan according to standard practice.
3) ICBT CT based optimized plan	This plan will start with the above described 2D plan and will be optimized to target the CT based HR-CTV (also informed by initial diagnostic imaging) with the same objectives as the GEC-ESTRO MRI guidelines.
4) GEC-ESTRO MRI based optimized plan	This plan will start with the above described 2D plan and will be optimized according to GEC-ESTRO guidelines taking into account the patient's initial diagnostic imaging as well as MRI scan with the applicator in place.

Each of the three treatment plans will be registered on the MRI, and the MRI contours will be used as the gold standard such that each treatment plan will be evaluated for its coverage of the HR-CTV and ability to meet constraints for the adjacent organs at risk. For each of the three treatment plans, we will evaluate the D90, D100, V100, V150, V200, for the HR-CTV and IR-CTV as well as the D0.1, 1, 2 cc for bladder, sigmoid, and rectum (see Table 2). Conformality index (CI=V100%/VCTV) and dose homogeneity index (DHI= (V100%-V150%)/V100%) will be calculated for HR-CTV.

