### Analysis

We will use summary statistics to describe the clinical and demographic characteristics of patients. We will similarly summarize the dosimetry parameters listed in Table 1 for each of the three planning methods noted above.

We will compare the HR-CTV D90, D2 cc bladder, and D2 cc rectum for the MRI based treatment plan (method #4) and CT based treatment plan (method #3) to the standard 2D plan (method #1) and the 2D plan informed by 3D imaging (method #2). We will use analysis of variance methods with Dunnett's procedure to compare the outcomes from each of planning methods with the outcomes from planning method #1. We will similarly compare the other dosimetry parameters between the various planning methods.

We will also keep track of the number of person-hours required for planning using each imaging modality by documenting the time spent generating contours on both CT and MRI and the amount of time spent generating each individual plan. Through the billing department, we will also capture the fees associated with the additional MRI and CT scan as well as the charge of the MRI compatible applicators for each patient and compare this to the fees for a routine implant in which a comparable standard applicator is used and MRI and CT at the time of implant are not obtained.

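### The study is sized on nine tests at 0.0056, but the Analysis section names ANOVA with Dunnett at no stated level and adds six contrasts with plan #2 that neither rule covers.

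*Combined protocol and SAP*

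**What the plan says.** All places are in the combined protocol and SAP.

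- **Sample Size (6.0).** Power is computed from paired differences in four pilot patients, using t-tests with n = 30 at two-sided 0.0056. The reason given is "We use the Bonferroni correction to the significance level since we are testing 3 methods" on three dosimetry parameters, so 0.05/9. The three methods are not named.
- **Primary Endpoint (6.0).** The goal is to learn whether 3D planning "allows for improved tumor coverage while respecting normal tissue constraints as compared to standard 2D treatment planning". This makes plan #1 the reference.
- **Analysis (6.0).** HR-CTV D90, D2cc bladder and D2cc rectum for plans #4 and #3 are compared "to the standard 2D plan (method #1) and the 2D plan informed by 3D imaging (method #2"). The method is analysis of variance "with Dunnett's procedure to compare the outcomes from each of planning methods with the outcomes from planning method #1". Neither a level nor Bonferroni is mentioned. The same section promises summaries "for each of the three planning methods noted above".
- **Table 1 (5.0, Dosimetric Treatment Planning Study).** Four plans are listed, the last being "4) GEC-ESTRO MRI based optimized plan".
- **How the plans are made (5.0).** Plan #2 is plan #1 after the physician sees the images "such that they may make subtle adjustments to the 2D treatment plan". Plan #3 starts from the 2D plan, and so does plan #4: "This plan will start with the above described 2D plan and will be optimized according to GEC-ESTRO guidelines".

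**The concern.** Three things do not fit together.

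1. The rule that sized the study (paired t, 0.0056) is not the rule named for the analysis (Dunnett, no level). Dunnett adjusts for several plans against one control within a single parameter. It does not adjust across the three parameters, which the Bonferroni split does. Run in the customary way at 5% for each parameter, it would drop part of the control that the Sample Size section promises.
2. The six contrasts of #3 and #4 with #2 have no rule, no level and no secondary label, although they use the three primary parameters.
3. Dunnett with one pooled error term assumes that all between-plan differences are equally variable. Plan #2 is a light edit of #1, while #3 and #4 are re-optimised from it, so equal variability is implausible.

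At stake is the verdict on modest differences. If the choice of rule is left open until the data are in, the same result can be called significant or not.

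**Working it through.** **The plan's own figures.** 0.05/9 = 0.00556, printed as 0.0056. Power for a paired t-test (noncentral t, n = 30, 29 df, two-sided 0.0056):
- D90: 273.75/303.69 = 0.90 SD gives 96.7% (printed 96%).
- Bladder and rectum: 0.80 SD gives 90.6% (printed 90%).

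A two-sample t-test with 30 per group would give 73% and 59%, so the sizing is paired.

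**Counting contrasts.**
- #2, #3 and #4 against #1, three parameters: 3 × 3 = 9. This matches both the Bonferroni count and the Dunnett family.
- #3 and #4 against #2, three parameters: 2 × 3 = 6.
- Total: 15, against nine allotted.

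**Critical values.**
- Paired t, 29 df, at 0.0056: 2.993.
- Dunnett, three contrasts, 87 error df (30 patients × 4 plans, repeated measures), 5% per parameter: 2.389, a per-contrast p of about 0.019.
- Dunnett at 0.05/3 per parameter: 2.812, a per-contrast p of about 0.006.

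**Where the rules disagree.** Threshold = critical value × SD/√30, using the pilot SDs from Sample Size and assuming that the pooled error matches them.

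| Parameter | SD (cGy) | SD/√30 | Dunnett 5% | Dunnett 0.05/3 | Paired t at 0.0056 |
|---|---|---|---|---|---|
| D90 | 303.69 | 55.45 | 132 | 156 | 166 |
| D2cc bladder | 250.81 | 45.79 | 109 | 129 | 137 |
| D2cc rectum | 194.44 | 35.50 | 85 | 100 | 106 |

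A mean difference between a Dunnett column and the last column is significant by Dunnett and not by the sizing rule.

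**Why pooling matters.** Let #3−#1 and #4−#1 have variance 1 and correlation 0.8, and let #2−#1 have SD 0.25, independent of both (all assumed). The pooled error reflects the mean variance of the six pairwise differences:

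(0.0625 + 1 + 1 + 1.0625 + 1.0625 + 0.4)/6 = 0.765

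The standard error used for #3 and #4 is then √0.765 = 0.87 of the true one, and the test is too liberal. With correlation 0 the 0.4 becomes 2 and the mean is 1.03, so the distortion depends on how alike #3 and #4 are.

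**Simulated family error.** All nulls true, n = 30, 20,000 runs per setting. Assumed: SD of #2−#1 is 0.1, 0.25 or 0.5 of that of #3−#1; correlation of #3−#1 with #4−#1 is 0, 0.5 or 0.8; #2−#1 is independent of both; parameter correlation is 0 or 0.6.

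| Rule | Chance of any false positive |
|---|---|
| Nine paired tests at 0.0056 | 3.9% to 5.1% |
| Fifteen paired tests at 0.0056 | 4.4% to 6.7% |
| Pooled Dunnett, 5% per parameter | 7% to 20% |
| Pooled Dunnett, 0.05/3 per parameter | 2% to 10% |

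With wider assumptions (parameter correlations of 0.3 and 0.9 added, and #2−#1 correlated 0.5 with the other differences), Dunnett at 5% runs from 5.0% to 23.1% and fifteen tests from 2.9% to 6.6%. With independent, equal-variance plans, where pooling is valid, Dunnett at 5% still gives 9% to 14% because nothing adjusts across parameters; fifteen tests give 4.8% to 7.6%.

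**Power if all fifteen are confirmatory.** 0.05/15 = 0.0033 gives 94.8% (D90) and 86.8% (0.80 SD).

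**The case against.** The best defence is that the two sections can be joined without conflict. Nine is exactly the size of the Dunnett family, so Dunnett at 0.05/3 per parameter would honour the overall 5%. The bands of disagreement then shrink to 156–166, 129–137 and 100–106 cGy. The 5% level is the reader's assumption, and so is pooling: the wording does not exclude a mixed model with unequal variances. All three powered effects (273.75, 200 and 155 cGy) and all three pilot means (459.91, 407.11 and 159.83 cGy) clear both rules. Much of the 7% to 20% comes from the organ doses or from false decreases in D90. A false D90 benefit against #1 under pooled Dunnett at 5% occurs in only about 1% to 4% of runs. Plans #3 and #4 are made for comparison and are not delivered.

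Most of this stands as a limit on severity. It does not close the gap. The plan states neither 0.05/3 nor an error structure, and with pooled errors even 0.05/3 can reach about 10%. The Sample Size section gives pilot data only for the MRI plan against the 2D plan, so smaller differences for #3 or #2 are quite possible, and those could fall within the bands. The goal set against standard 2D planning suggests that the #2 contrasts are supportive, but the plan never says so.

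**Conclusion.** The point holds; the change should be made, but it does not threaten the study. The decision rule is undefined. The sizing rule keeps the family error near 5%, whereas the named method, as commonly run, does not: 7% to 20% in the main simulations. That range rests on a 5% level per parameter, a pooled error, and correlations and SD ratios that the documents do not give. The main exposure is the Dunnett level. The six extra contrasts at 0.0056 add little or nothing. If D90 is tested at 0.0056, the benefit claim is protected: five D90 contrasts together carry 1.6% to 2.3%. The study is not undersized. The mismatch between three plans in the text and four in Table 1 is minor by itself, but it leaves the nine hypotheses unnamed.

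**What to change.** Replace the ANOVA/Dunnett sentence with one family and one rule, for example: *For HR-CTV D90, D2cc bladder and D2cc rectum, plans #2, #3 and #4 are each compared with plan #1 by a paired t-test (nine tests), using Holm's procedure at an overall two-sided 5%. Comparisons of #3 and #4 with #2 are secondary and are reported with 95% confidence intervals.*

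Holm's first step is 0.05/9 = 0.0056 and its later steps are less strict, so n = 30 and the printed powers remain as minimums. In simulation with plans derived from #1, its family error is 2.9% to 5.0%. The cost is SAP wording only, and the comparisons with #2 carry no confirmatory claim.

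If those comparisons are to be confirmatory, test all fifteen at 0.0033 and restate power as about 95% (D90) and 87% (0.80 SD effects), a loss of about 2 and 4 points.

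If Dunnett is preferred, state its level, including how the three parameters share the 5%, and use paired or covariance-aware errors.

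In either case, name the three methods in the Sample Size section and reconcile the references to three plans with the four in Table 1.

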### Analysis

We will use summary statistics to describe the clinical and demographic characteristics of patients. We will similarly summarize the dosimetry parameters listed in Table 1 for each of the three planning methods noted above.

We will compare the HR-CTV D90, D2 cc bladder, and D2 cc rectum for the MRI based treatment plan (method #4) and CT based treatment plan (method #3) to the standard 2D plan (method #1) and the 2D plan informed by 3D imaging (method #2). We will use analysis of variance methods with Dunnett's procedure to compare the outcomes from each of planning methods with the outcomes from planning method #1. We will similarly compare the other dosimetry parameters between the various planning methods.

We will also keep track of the number of person-hours required for planning using each imaging modality by documenting the time spent generating contours on both CT and MRI and the amount of time spent generating each individual plan. Through the billing department, we will also capture the fees associated with the additional MRI and CT scan as well as the charge of the MRI compatible applicators for each patient and compare this to the fees for a routine implant in which a comparable standard applicator is used and MRI and CT at the time of implant are not obtained.

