#### Secondary objectives

1. Determine if MRI imaging is superior to CT imaging in delineating a high risk target volume.
2. Identify clinical and tumor characteristics of patients in whom CT or MRI can improve dosimetric tumor coverage and normal tissue sparing.
3. Evaluate the feasibility of MRI-based treatment planning utilizing the shielded MD Anderson adaptive applicator.
4. Compare resource utilization for MRI and CT based treatment planning as compared to standard film based planning techniques.

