It is important to clarify the magnitude of potential benefit from these new approaches because utilization of 3D image-based treatment planning is substantially more expensive than standard planning; one study reported increased costs of 10-15% to setup 3D image based gynecologic brachytherapy. MRI in particular, despite its potential benefits, is expensive, logically difficult and is not as widely available for radiation oncology treatment planning as CT imaging. It also requires the use of specially-designed MRI-compatible applicators. As a result, Viswanathan and colleagues suggested a standardized approach to CT-based contouring. When the authors compared CT with MRI, they found that CT was adequate for analysis of the doses to organs at risk, but that CT-based standardized contours tended to overestimate tumor width, leading to significant differences in target coverage. While this study is the only published series comparing CT to MRI, it included only 10 patients with a single radiation oncologist responsible for the contouring. Additionally, the CT quality was poor (with 4 mm slice thickness) compared to current standards (typically 1-2 mm slice thickness). To date, there are no studies evaluating the role of modern CT scanning in an adequate number of patients to determine if there is a select group in which CT may be equivalent to MRI in delineating a target volume.

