#### Dosimetric Contouring Study

As part of the lab based portion of this protocol, the MRI and CT images will be uploaded into our brachytherapy treatment planning software, Oncentra. After reviewing the patient's initial diagnostic imaging and physical examination at the time of diagnosis and the time of implant the radiation oncologist involved in the procedure and one additional radiation oncologist will contour a HR-CTV based on the GEC-ESTRO guidelines (Appendix E) on the CT followed by the MRI. One of the primary investigators will also contour a HR-CTV as well as critical structures (rectum, bladder, sigmoid colon) on both the MRI and CT scan. The 2D plan will then be registered on the MRI and CT within the treatment planning software. Based on the primary investigators approved contours several additional plans will be created for purpose of comparison (See Table 1).

The contours devised by all three physicians on MRI and CT will also be compared to determine the interobserver variability for each specific imaging modality. Contours will be imported into Computerized Environment for Radiation Research (CERR), an open-source MATLAB (TheMathWorks, natick, MA) - based radiation therapy planning analysis tool. The "apparant agreement" method will be used to calculate the apparent volume overlap such that a volume - agreement cumulative histogram can be generated.

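### Secondary objective 1 asks whether MRI outlines the target better than CT, but no between-modality analysis is specified for it

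*Combined protocol and SAP*

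**What the plan says.** Section 1.0 lists as the first secondary objective: "Determine if MRI imaging is superior to CT imaging in delineating a high risk target volume". That is a head-to-head question about contouring.

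Four places in the plan bear on it.

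- **Section 6.0, Analysis, key parameters.** For HR-CTV D90, bladder D2cc and rectum D2cc, the plan compares the MRI plan (#4) and the "CT based treatment plan (method #3) to the standard 2D plan (method #1) and the 2D plan informed by 3D imaging (method #2"). The stated procedure is analysis of variance "with Dunnett's procedure to compare the outcomes from each of planning methods with the outcomes from planning method #1".
- **Section 6.0, Analysis, remaining parameters.** "We will similarly compare the other dosimetry parameters between the various planning methods". No pairs are named.
- **Section 5.0, Dosimetric Contouring Study.** "The contours devised by all three physicians on MRI and CT will also be compared to determine the interobserver variability for each specific imaging modality". An apparent-agreement method yields a histogram of volume against agreement. Two of the three observers contour CT first and MRI second.
- **Section 5.0, Dosimetric Treatment Planning Study.** One reference is named for scoring: "the MRI contours will be used as the gold standard such that each treatment plan will be evaluated for its coverage of the HR-CTV".

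The Secondary Endpoint part of section 6.0 covers planning time, imaging time and fees. Section 6.0 contains no contour analysis.

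**The concern.** Dunnett's procedure is a many-to-one method. With #1 as control it gives #2, #3 and #4 each against #1, and nothing between #3 and #4. On the contouring side, two separate summaries of observer agreement, one per modality, do not estimate the difference between them. The objective therefore has no defined endpoint, contrast or interval.

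The gap matters because the Background presents this question as open. It reports that 70% of survey respondents used CT and 2% used MRI. It describes the one published CT-MRI comparison as having 10 patients, a single contouring oncologist and 4 mm slices.

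Without a stated contrast, a report could call MRI superior because #4 differs significantly from #1 and #3 does not, even if #3 and #4 hardly differ. It could equally call CT adequate because both beat the 2D plan. A difference in significance is not a test of the difference.

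**Working it through.** **1. Which pairs are covered?**

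| Measure | Pairs specified | MRI against CT? |
|---|---|---|
| HR-CTV D90, bladder D2cc, rectum D2cc | #3 and #4, each with #1 and #2; Dunnett with #1 only | No |
| Remaining dose parameters | Not named | Possible, not stated |
| HR-CTV contours, three observers | Variability within each modality | No contrast stated |
| Time and fees | Compared with each other and with 2D | Yes, but this is resource use |

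**2. The plan's own power figure.** Inputs from Sample Size: n = 30, D90 effect 273.75 cGy (20% of 1368.73), SD of the paired MRI minus 2D difference 303.69 cGy (4 pilot patients), two-sided level 0.0056. The noncentrality is (273.75/303.69) × √30 = 4.94 on 29 degrees of freedom, giving power of 96.7%. The stated 96% reproduces. The only D90 effect specified is MRI against 2D.

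**3. Precision of a within-patient #4 minus #3 difference in D90.** The documents give no SD for this difference. The range below is an assumption: 150 cGy as an illustrative lower value, and the pilot MRI minus 2D SD of 303.69 cGy as the upper. The 95% half-width is t(0.975, 29) × SD/√30, with t = 2.045.

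- SD 303.69: 2.045 × 303.69/5.477 = 113 cGy; 113.4/1368.73 = 8.3%.
- SD 150: 2.045 × 150/5.477 = 56 cGy; 56.0/1368.73 = 4.1%.

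**4. Precision of the agreement contrast.** No SD is given for agreement either, so only SD units are possible. With 30 patients the half-width is 2.045/√30 = 0.37 SD.

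The restriction to the adaptive shielded ovoid applies to the primary analysis, and nothing extends it to this objective. The accrual target reproduces as 30/(0.75 × 0.70) = 57.1. Without the applicator restriction, 57 × 0.75 = 42.75, or about 43 patients, would have both scans if the plan's assumptions hold. The half-width is then 2.018/√43 = 0.31 SD.

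**5. Cost if the dose contrasts were tested inside the Bonferroni family.** Three more tests make 12, and 0.05/12 = 0.0042. Power for MRI against 2D on D90 falls from 96.6% (at 0.05/9) to 95.7%, and for a 0.80 SD effect from 90.6% to 88.5%. As secondary estimates with intervals, the contrasts cost nothing here.

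**6. What each contrast can show.** Plan #4 is optimized on the MRI contours and then scored on them. Plan #3 is optimized on CT contours and scored on the MRI ones. So #4 minus #3 takes MRI as the truth. Its direction for D90 alone is not guaranteed: the Background reports that CT contours tended to be too wide, and planning to a wider target could raise D90 on the MRI volume. The agreement contrast does not use MRI as the reference, but it measures consistency between observers rather than correctness. For two of the three observers it also mixes modality with order.

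**The case against.** The strongest reply is that the plan does bring CT and MRI together. The CT plan is scored directly on the MRI contours, three observers contour on both modalities, and the general sentence on the remaining parameters can be read to include #3 against #4. This stands. A reader might infer that the plan never sets CT against MRI anywhere, and the documents do not support that. What is missing is a stated contrast on the key dose measures and on contour agreement.

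Three other stronger readings also go too far.

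- A reader might infer that MRI superiority would have to be deduced from the separate comparisons with 2D. No section says so. The contouring study is the nearest analysis, and how results would be read is conjecture.
- A reader might infer that the plan fails an equivalence aim. The Background does note the lack of studies "to determine if there is a select group in which CT may be equivalent to MRI in delineating a target volume", but no equivalence objective is listed and no margin is given.
- A reader might infer that adding #4 minus #3 on D90 would settle the objective. With MRI contours as the reference, it would not.

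It is also fair to say that this is a secondary objective, that plans #3 and #4 are not used for treatment, and that the primary comparison with 2D is unaffected. These limit the seriousness of the point but leave the gap in place.

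**Conclusion.** The point holds in a limited form: secondary objective 1 poses a direct MRI-versus-CT question about outlining the target, and no between-modality analysis is specified for it. Followed as written, the plan gives no CT-MRI contrast on D90, bladder D2cc, rectum D2cc or observer agreement.

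The data to be collected allow one. For D90 the half-width of 56 to 113 cGy rests on 30 patients and an assumed SD of 150 to 304 cGy; the upper value is borrowed from an MRI minus 2D difference in 4 patients. A larger SD would widen it in proportion. That figure describes precision on a dose consequence, not on quality of delineation. Precision for agreement cannot be put in natural units from the documents.

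The trial can support a statement about reproducibility between observers and about the dose consequence of planning on CT if MRI is taken as correct. Neither shows that MRI contours are more accurate.

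**What to change.** Add a short analysis for secondary objective 1 to section 6.0.

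1. **Main analysis.** The within-patient MRI minus CT difference in three-observer apparent agreement on the HR-CTV, with a 95% confidence interval, in all patients with both scans contoured. Name in advance the single per-patient summary taken from the agreement histogram. State that the result supports a claim about reproducibility, not accuracy. Either vary the CT/MRI contouring order across patients, or state that order is confounded with modality.
2. **Supportive analysis.** The within-patient #4 minus #3 differences in HR-CTV D90, bladder D2cc and rectum D2cc, with 95% intervals. State that all plans are scored on MRI contours, so this measures the dosimetric consequence of planning on CT if MRI is taken as truth and cannot by itself establish superior delineation.
3. **Interpretation rule.** State that neither conclusion is drawn from comparing the significance of #3 and #4 against #1.

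The cost is a few lines of text and a little more analysis. All contours and plans are already produced, and as secondary estimates these leave the 0.0056 level unchanged. Varying the contouring order would change the contouring procedure but needs no extra scans.
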